5.1.3.1 Prior therapies date imputation

See Section 5.1.3.

5.1.3.2 Post therapies date imputation

See section 5.1.3.

5.2 AEs coding/grading

AEs will be coded according to MedDRA dictionary. The MedDRA version used for reporting will be described in the footnotes.

Safety topics of interest, defined in the Safety Profiling Plan are defined in the Program Case Retrieval Sheet. Missing severity will be assumed to be severe in the summary table.

Hypoglycemia classification is presented in Table 5-1.

Table 5-1 Hypoglycemia classification

Category	Definition	Criteria as specified in the Hypo eCRF
Severe hypoglycemia	An event, requiring assistance of another person (third party assistance) to actively administer carbohydrate, glucagon, or other corrective actions, confirmed or not by a BG measurement	An event with answer = 'YES' for any one of the two questions: 
• Was third party assistance required?• Was medical assistance received?

Category	Definition	Criteria as specified in the Hypo eCRF
Other clinically significant hypoglycemia	Plasma glucose < 3.0 mmol/l (54 mg/dl)* with or without typical symptoms of hypoglycaemia, and which is handled by the subject himself/herself.	An event with answer = 'YES' to the question 'Glucose measurement taken' and the plasma glucose < 3.0 mmol/l (54 mg/dl), and answer = NO to both questions: 
• Was third party assistance required?• Was medical assistance received?

*Blood glucose values need to be converted to plasma glucose values.

A plasma glucose of 3.0 mmol/L (54 mg/dL) corresponds to a whole blood glucose of 2.7 mmol/L (48 mg/dL)

Plasma glucose = blood glucose * 1.12.

5.3 Laboratory parameters derivations

Not applicable

5.4 Rule of exclusion criteria of analysis sets

Criteria defining protocol deviations are referenced in the "Protocol Deviations" tab of the Data Review Plan document. Protocol deviations will be classified into 5 categories as appropriate:

- Selection criteria not met
- Treatment deviation
- Prohibited concomitant medication
- Subject not withdrawn as per protocol
- Other

The protocol deviations leading to the exclusion of patients from analysis sets are outlined in Table 5-2. In addition, the non-protocol deviation criteria leading to the exclusion of patients from analysis sets are outlined in Table 5-3. Table 5-2 and Table 5-3 may be updated according to Data Review Plan document before data base lock.

Table 5-2 Protocol deviations leading to exclusion of patients from analysis sets

Deviation ID	Description of Deviation	Exclusion from Analysis set(s)
INCL01a	Informed consent not obtained	SCR, ENR, RAN, FAS,
INCL01b	Informed consent not signed	SAF
OTH07	Misrandomized in IRT	FAS

Table 5-3 Non-protocol deviation criteria leading to exclusion of patients from analysis sets

Description of Deviation	Exclusion from Analysis set(s)
No study drug taken during double-blind	SAF

5.5 Search criteria for the anti-diabetic medications by type:

 Combos – Codes match.pptx  List of ingredients_anti

Category	Type	ATC code or drug code
Insulin	All insulin A10A	A10A (all insulin), and within this group: A10AB, A10AC, A10AD, A10AE and A10AF
OADs – used as single pills	Metformin	A10BA Biguanides
	SU	A10BB Sulfonylureas A10BC Sulfonamides (heterocyclic)
	AGIs	A10BF Alpha glucosidase inhibitors
	TZDs	A10BG Thiazolidinediones
	DPP-4i	A10BH Dipeptidyl peptidase 4 (DPP-4) inhibitors
	GLP-1 analogues	A10BJ Glucagon-like peptide-1 (GLP-1) analogues
Combinations of OADs	See details in the above pptx document Combos – Codes.pptx. Exclude Metformin + SGLT-2i and DDP-4i + SGLT-2i for this study	
Other		A10BX Other

6 Reference

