  - Barrier methods of contraception: condom or occlusive cap (diaphragm or cervical/vault caps). For UK: with spermicidal foam/gel/film/cream/vaginal suppository.
  - Use of oral, (estrogen and progesterone), injected or implanted hormonal methods of contraception or other forms of hormonal contraception that have comparable efficacy (failure rate <1%), for example hormone vaginal ring or transdermal hormone contraception or placement of an intrauterine device (IUD) or intrauterine system (IUS).

In case of use of oral contraception women should have been stable on the same pill for a minimum of 3 months before taking investigational drug.

Women are considered post-menopausal and not of child bearing potential if they have had 12 months of natural (spontaneous) amenorrhea with an appropriate clinical profile (e.g. age appropriate, history of vasomotor symptoms) or have had surgical bilateral oophorectomy (with or without hysterectomy), total hysterectomy or tubal ligation at least six weeks ago. In the case of oophorectomy alone, only when the reproductive status of the woman has been confirmed by follow up hormone level assessment is she considered not of child bearing potential.

If the above wording is not in line with specific country regulations, exclusion criteria for women of child-bearing potential will be managed locally and in line with those regulations.

8. Type 1 diabetes, monogenic diabetes, diabetes resulting from pancreatic injury, or secondary forms of diabetes (e.g. Cushing's syndrome or acromegaly-associated diabetes).
9. Use of SGLT2 inhibitors within 2 months of Visit 1, or between Visit 1 and Visit 201 (randomization).
10. Self-measured FPG > 12.2mM (220mg/dL) on two occasions in the week prior to randomization (Visit 201).
11. History of ketoacidosis, lactic acidosis, or hyperosmolar coma, or any of these occurring between Visit 1 and Visit 201 (randomization).
12. Symptomatic genital infection or UTI in the 4 weeks prior to Visit 1, or between Visit 1 and Visit 201 (randomization).
13. GI disorders associated with chronic diarrhea.
14. Myocardial infarction (MI), stroke, surgery for heart disease, percutaneous coronary intervention (PCI) in the 3 months prior to Visit 201 (randomization).
15. Unstable angina within 3 months of Visit 1, or between Visit 1 and Visit 201 (randomization).
16. Isolated right HF due to pulmonary disease.
17. Dyspnea and/or edema from non-cardiac causes, such as lung disease, anemia, or severe obesity.

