**Table 5-2 Prohibited medication**

Medication/product	Prohibition period	Action taken
St. John's wort (strong CYP3A inducer)	Entire study (from V1 until end-of-study)	Discontinue treatment during the screening period once patient is eligible for participation in the study.
SGLT inhibitors other than study medication	Entire study (and up to 2 months before Visit 1)	SGLTi has to be stopped immediately, otherwise the patients has to be discontinued from study medication

Some medications or products must be used with caution:

- Use of grapefruit juice (strong inhibitor of CYP3A4) should be discouraged and its consumption must not happen within 2h of study medication intake.
- Use of antibiotic or antifungal medications that are strong inhibitors of CYP3A4 should be limited to 10 days during the study and must not be used at the time of randomization. Examples of such medications are clarithromycin, telithromycin, itraconazole, ketoconazole, voriconazole or posaconazole.
- Use of UGT inhibitors such as probenecid, valproic acid or mefenamic acid should be limited to 10 days during the study and must not be used at the time of randomization.

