2.4.2 Prior, concomitant and post therapies

Prior medications are defined as any recorded medication taken and stopped prior to the date of the first dose of the double-blind study drug.

Concomitant medications for the double-blind period are any medications given at least once between the day of first dose of double-blind study medication and the end of the double-blind period, including those which started pre-BL and continued into the treatment period.

Similarly, prior non-drug therapies are defined as any recorded non-drug therapy taken and stopped prior to the date of the first dose of the double-blind study drug. Concomitant non-drug therapies for the double-blind period are defined as any recorded non-drug therapy given between the day of first dose of double-blind study medication and the end of the double-blind period.

Prior and concomitant medications will be summarized separately by ATC, PT and treatment group. Prior and concomitant non-drug therapies will be summarized separately by primary SOC, PT and treatment group.

The number and percentage of patients meeting rescue criteria and taking rescue medication, and duration of exposure to rescue medication during double-blind period will be summarized by treatment group.

The number and percentage of patients on anti-diabetic medications at baseline (randomization visit) will be summarized by treatment group and medication types as follows:

- Any anti-diabetic medication (insulin or OADs)
 - Insulin
 - OADs (used as single pills)
 - Metformin
 - SU - Sulfonylureas (including Sulfonamides)
 - AGIs
 - TZDs
 - DPP-4 inhibitors
 - GLP-1 analogues
 - Combination of OADs
 - Phenformin + SU
 - Metformin + SU
 - Metformin + TZD
 - SU + TZD
 - Metformin + DPP-4 inhibitor
 - Metformin + AGI
 - DPP-4 inhibitor + TZD
 - Other

The search criteria for the anti-diabetic medications by type are included in [Appendix 5.5](#).

The use of prohibited medications, defined in [Table 2-2](#), will also be summarized.

Table 2-2 Prohibited medication for reporting

Prohibited Medication	Drug record No. or ATC
SGLT2 inhibitors	A10BK
Clarithromycin	00984601
Telithromycin	01548701
Itraconazole	00780701
Ketoconazole	00532501
Voriconazole	01510101
Posaconazole	01762801
Probenecid	00045101
Valproic Acid	00228501
Mefenamic Acid	00044201

The SAF will be used for the above analyses.

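### SAP Table 2-2 searches for prohibited SGLT inhibitors under A10BK alone, so the prohibited-medication summary can under-count combination pills that protocol Table 5-2 also prohibits

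*SAP*

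**What the plan says.** **Protocol.** Table 5-2 names the prohibited class as "SGLT inhibitors other than study medication", for the entire study and for up to 2 months before Visit 1. It draws no line between single-agent and combination products. Exclusion criterion 9 in protocol 4.2 covers "Use of SGLT2 inhibitors within 2 months of Visit 1, or between Visit 1 and Visit 201 (randomization").

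**SAP 2.4.2** sets out three medication outputs that bear on this point:

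- A general summary: "Prior and concomitant medications will be summarized separately by ATC, PT and treatment group". Concomitant covers anything given at least once in the double-blind period.
- A baseline anti-diabetic table: "The number and percentage of patients on anti-diabetic medications at baseline (randomization visit) will be summarized by treatment group and medication types as follows". Its search rules are in the appendix: "The search criteria for the anti-diabetic medications by type are included in" SAP 5.5.
- A prohibited-medication summary, introduced by "The use of prohibited medications, defined in" Table 2-2. The only SGLT row in that table reads "SGLT2 inhibitors A10BK".

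**SAP 5.5** assigns A10B subclasses (A10BA, A10BB, A10BC, A10BF, A10BG, A10BH, A10BJ) to anti-diabetic drugs taken as single pills. Combination products are a separate row, identified through an embedded code file. That row carries the instruction "Exclude Metformin + SGLT-2i and DDP-4i + SGLT-2i for this study".

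**The concern.** The prohibited-medication summary is meant to show, by arm, how often patients took something the protocol bars. Another SGLT inhibitor is the most consequential entry on that list because it shares its mechanism with LIK066 and with empagliflozin. Use in the placebo arm would dilute the NT-proBNP, HbA1c, weight and blood pressure contrasts. Use in an active arm would mean two SGLT inhibitors at once. A reader judging either possibility will look first at the SGLT row of this summary.

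If that row finds only single-agent products, a patient on a metformin plus SGLT-2 inhibitor pill, or a DPP-4 inhibitor plus SGLT-2 inhibitor pill, is not counted there. The SAP leaves little else that is designed for the purpose. The per-protocol set and its sensitivity analysis in protocol 9.1 and 9.4.4 are not carried into SAP 2.2 and 2.5.4. SAP Table 5-2 removes patients from analysis sets only for consent failures and misrandomization.

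**Working it through.** No arithmetic applies. The check traces each output to its search rule and asks what happens to a combination pill containing an SGLT-2 inhibitor.

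**Step 1: scope of the prohibition against scope of the search.** Protocol Table 5-2 covers all non-study SGLT inhibitors. SAP Table 2-2 covers one ATC class and labels the row SGLT2 inhibitors, which is narrower wording than the protocol's. The other nine rows of Table 2-2 are searched by drug record number. None of them concerns an SGLT inhibitor.

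**Step 2: does A10BK include combinations?** Neither document says so directly, and A10BK does not appear in SAP 5.5. The layout of 5.5 is the evidence. There, A10B subclasses stand for single pills, and combinations need their own code file. The two SGLT-2 inhibitor pairs are dealt with in the combinations row, so the SAP handles them as combination products. If A10BK follows the same pattern as its sister subclasses, it does not capture them. The combination-code file and the ingredient list are embedded in the SAP and not reproduced, so this remains an inference.

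**Step 3: coverage by output.**

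| Output | Rule | Combination pill started after randomization | Combination pill taken at randomization |
|---|---|---|---|
| Concomitant medications | ATC, preferred term, arm; no SGLT exclusion | Listed, not flagged as prohibited | Listed if continued into the double-blind period |
| Prohibited medications | Table 2-2: A10BK | Probably not counted | Probably not counted |
| Anti-diabetic medications at baseline | SAP 5.5 | Outside the table's time point | Left out of the combination categories by the exclusion |
| Protocol deviations | Data Review Plan, not shown | Cannot be determined | Cannot be determined |

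**Step 4: what the 5.5 exclusion governs.** SAP 2.4.2 cites 5.5 for the anti-diabetic types at the randomization visit, before it introduces Table 2-2. Nothing links the exclusion to the prohibited-medication search or to the general medication table. The exclusion agrees with the combination categories listed in 2.4.2, none of which names an SGLT-2 inhibitor pair, and with exclusion criterion 9. Its consequence is limited. A patient randomized in breach of that criterion while on such a pill would not be shown in the baseline combination categories, and the SAP does not say where the record goes instead.

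There are therefore two adjacent gaps with separate causes: the missing codes in Table 2-2, and the unrouted exclusion in 5.5.

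**The case against.** The strongest reply is that these pills are not lost. Protocol 5.5.7 requires all medications after enrollment to be recorded, and the general concomitant-medication table would list them by ATC class, preferred term and arm. That is correct. A reader might infer from the exclusion wording that SGLT-2 inhibitor combination pills are counted in no medication table. The documents do not support that, because the exclusion belongs to the baseline anti-diabetic table alone. What remains is that the general table does not mark the pills as prohibited or add them to the SGLT row, so a reader would have to find and total separate preferred terms.

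A second reply is that other routes exist. SAP 5.4 has a deviation category for prohibited medication, and SAP 2.3.1 summarizes deviations and reasons for discontinuation by arm. These may help but cannot be relied on. The deviation sentence can be read as limited to deviations that lead to exclusion from an analysis set, and prohibited medication is not among those in SAP Table 5-2. Protocol Table 5-2 ties discontinuation of study drug to a failure to stop the other SGLT inhibitor, so discontinuation counts need not show every user.

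A third reply is that the single-agent reading of A10BK is unproven. It is an inference, and it would be wrong to say that every user of such a pill is certainly missed.

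Finally, the study ended early, the SAP supports an abbreviated report, and the NT-proBNP MMRM is exploratory. The summary feeds no estimate. This limits the weight of the point but does not remove it.

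**Conclusion.** The point holds in a narrow form. The search rule stated in SAP Table 2-2 is narrower than the prohibition in protocol Table 5-2, and on the SAP's own layout it probably misses fixed-dose combinations. The prohibited-medication summary can therefore under-count SGLT inhibitor use by arm. Separately, SAP 5.5 drops two SGLT-2 inhibitor combinations from the baseline categories without saying where those records are counted.

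The size cannot be given. The documents contain no rate of SGLT inhibitor use, and the class is both an exclusion at entry and prohibited afterwards, so the number may be small or zero.

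A reader might also infer that the code list biases the efficacy comparisons. It does not. Any dilution would come from the drug use itself, and the MMRM on the full analysis set neither censors nor excludes on this table. What is affected is a descriptive count, and with it the reader's ability to judge contamination.

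The conclusion assumes that A10BK is used as a single-agent class, as the other A10B subclasses in 5.5 are, and that the embedded files do not already extend the Table 2-2 search.

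**What to change.** 1. In SAP Table 2-2, rename the row SGLT inhibitors, to match protocol Table 5-2. Define it as A10BK plus every combination product that contains an SGLT inhibitor, found by ingredient or through the combination codes already attached to SAP 5.5.
2. In SAP 5.5, state that the exclusion of the two SGLT-2 inhibitor pairs applies only to the baseline combination categories, and that the excluded records are counted in the prohibited-medication table.

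The cost is one code-list row and one sentence, plus a small programming change. No new data are needed, because the medications are already recorded. If the embedded files show that combinations are already captured for Table 2-2, a line saying so is enough for the first item.
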